2.1.1. Primary Estimand(s)

The primary estimand is intended to provide a population level estimate of the well state as well as changes in symptoms and voice features from well to sick in symptomatic SARS-CoV-2, Influenza virus or RSV positive participants using Electronic diary. This estimand (Estimand E1) is defined according to the primary objective and is in alignment with the primary endpoints. It includes the following 4 attributes:

- Population: Participants who are ≥ 18 years of age as defined by the inclusion and exclusion criteria, initially are SARS-CoV-2/Influenza/RSV negative and have no acute symptoms, and have potential to develop symptomatic SARS-CoV-2, Influenza virus or RSV illness.

- Variables: (1) Change in self-reported symptom scores in the Electronic diary from well to sick in symptomatic SARS-CoV-2, Influenza virus or RSV positive participants; (2) Change in voice features, such as pitch, jitter, harmonicity, entropy, flatness, shimmer from the voice collection as captured by the Electronic diary from well to sick in symptomatic SARS-CoV-2, Influenza virus or RSV positive participants.
- Intercurrent event(s):
 - There are no particular intercurrent events considered. Participants who have events that lead to missing data will be included and missing data will not be imputed.
 - Inadequate compliance – participants’ data will be used as recorded.
- Population-level summary: The well state characteristics as well as changes in symptoms and voice features from well to sick in symptomatic SARS-CoV-2, Influenza virus or RSV positive participants using Electronic diary.

2.1.2. Secondary Estimand(s)

The secondary estimand of this study is to provide a population level estimate of the percentage of occurrence for the compliance, quality of voice recordings, infection rates and feasibility of self-swabbing. This estimand (Estimand E2) is defined according to the secondary objectives and is in alignment with the secondary endpoints. It includes the following 4 attributes:

- Population: Participants who are ≥ 18 years of age as defined by the inclusion and exclusion criteria.
- Variables: All secondary endpoints, when appropriate.
- Intercurrent event(s):
 - There are no particular intercurrent events considered. Participants who have events that lead to missing data will be included and missing data will not be imputed.
 - Inadequate compliance – participants’ data will be used as recorded.
- Population-level summary: The percentage of occurrence for the endpoints.

CCI

- CCI [REDACTED]
- [REDACTED]
- [REDACTED]
- [REDACTED]

2.2. Study Design

This is a low-interventional, observational study with planned enrollment of approximately 8,700 participants 18 years of age or older in order to collect a total N=100 participants with (1) RT-PCR confirmed negative SARS-CoV-2, influenza virus and RSV (swab #1) and (2) RT-PCR confirmed positive SARS-CoV-2, influenza virus and RSV (swab #2 or any subsequent swab) symptomatic completers.

Each participant will be required to stay in the study for 6 weeks. If the participant tests positive for any of the three viruses at swab #1 or swab #2, they will continue the study until the end of Week 8.

[figure not shown]
Participants will record acute respiratory illnesses and SARS-CoV-2 symptoms and voice data daily for up to a maximum of 8 weeks in both the well state and, should they become ill, the sick state, utilizing the Electronic diary on their Mobile application. Once enrolled, the participant will start recording symptoms and voice in the Electronic diary, with daily time commitment to this portion of the study expected to be 2-4 minutes. Two nasal self-swab collection kits will be ordered for delivery to the participant once they are enrolled in the study. The participant will be asked to self-swab when the test kit arrives (swab #1). The kit, including the specimen, will be returned to the central lab for RT-PCR SARS-CoV2/Influenza/RSV RT-PCR testing. The participant is expected to complete 3 phonemes and 5 lines of reading each day, in addition to score the self-reported symptoms in the Electronic diary. If participants become sick (self-report) with new or increased symptoms of respiratory illness, they will be asked to self-swab (swab #2) and return the sample for central SARS-CoV-2/Influenza/RSV RT-PCR testing. If the participant does not develop any

new or increased symptoms between swab #1 and end of Week 6, they will obtain a self-swab (swab #2) at Day 42.

If the participant tests positive for any of the three viruses at swab #1 or swab #2, they will continue the study until end of week 8. If they test negative for the three viruses at swab #1 and swab #2, they will exit the study at approximately the end of week 6 when the test results are returned. The results of the RT-PCR testing will be shared with participants.

Demographic, medical history, and smoking status data will be collected. At the end of the study, voice and symptom trajectories will be analyzed to understand the SARS-CoV-2/influenza virus/RSV respiratory disease trajectories. Analysis of changes in symptoms and voice characteristics will be stratified by SARS-CoV-2/Influenza/RSV test results.

Figure 1. Schema for AcRIS Study Design

3. ENDPOINTS AND BASELINE VARIABLES: DEFINITIONS AND CONVENTIONS

3.1. Primary Endpoint(s)

The primary endpoints for this study are:

(a) *Change in self-reported symptom scores in the Electronic diary from well to sick in symptomatic participants with RT-PCR confirmed SARS-CoV-2, influenza virus, or RSV.*

(b) Change in voice features, such as pitch, jitter, harmonicity, entropy, flatness, shimmer from the voice collection as captured by the Electronic diary from well to sick in symptomatic participants with RT-PCR confirmed SARS-CoV-2, influenza virus, or RSV.

3.2. Secondary Endpoint(s)

The endpoints linked to each secondary objective are as follows:

Endpoints for secondary objective 1: *(a) Percentage of total days of symptoms; (b) Percentage of total days of voice recordings entered in the Electronic diary.*

Endpoints for secondary objective 2: *Percentage of quality voice recordings based on signal to noise ratio, sound duration and background noise measures.*

Endpoints for secondary objective 3: *Percentage of participants with SARS-CoV-2; and/or Influenza; and/or RSV RT-PCR based positivity in self-swabs.*

Endpoints for secondary objective 4: *(a) Percentage of participants administering the self-swab at self-swab #1 and self-swab #2. (b) Percentage of participants reporting symptoms in the Electronic diary, who have a self-swab collected at or around symptom onset. (c) Percentage of self-swabs with valid (positive or negative) or invalid (non-reportable due to technical or self-collection failure) results.*

CCI [REDACTED]

3.4. Baseline Variables

Demographic variables will be summarized. Age and gender may be used to investigate symptoms and voice features in four groups (Male >60 y/o; Male <=60 y/o; Female >50 y/o; Female <=50 y/o). Race may be included as a covariate in the analyses.

The enrollment questionnaire will be summarized. The following components of the enrollment questionnaire may be considered to stratify groups or be included as covariates:

- Current symptoms associated with respiratory infection, such as cold and flu; asthma and allergies

- Pre-existing medical conditions (yes/no)
- Current symptoms associated with pre-existing conditions (yes/no)
- Smoking status and frequency

3.5. Safety Endpoints

Safety profile of self-administered nasal swabs for SARS-CoV2/Influenza/RSV RT-PCR among participants: Incidence and severity of adverse events (AEs)/research related injuries (RRIs) among all enrolled participants.

4. ANALYSIS SETS (POPULATIONS FOR ANALYSIS)

Data for all participants will be assessed to determine if participants meet the criteria for inclusion in each analysis population prior to releasing the database and classifications will be documented per standard operating procedures.

Population	Description
Full Analysis Set (FAS)	All participants who sign the informed consent document and enroll in the study. Qualified participants are males or females aged 18 years and older (or the minimum state-specific age of consent if > 18) at Screening visit, who are willing and able to comply with daily symptom and voice assessments on the Electronic diary application and other study procedures including self-collection of nasal swabs, are expected to be available for the duration of the study, and are capable of giving informed consent.
Primary Analysis set	Participants in FAS who initially are SARS-CoV-2, Influenza and/or RSV negative and have no acute symptoms.
CCI	

5. GENERAL METHODOLOGY AND CONVENTIONS

An interim analysis will be performed once the first 1000 participants have completed the study (See [Section 7](#)). The study will continue whilst the interim analysis is being conducted.

A second interim analysis will be performed on Cohort 1 data, consisting of approximately 9100 participants enrolled by 15 Feb 2022 prior to Protocol Amendment 2. The study will continue whilst the second interim analysis is being conducted.

The primary analysis will be performed after the study is completed and final database is locked.

5.1. Hypotheses and Decision Rules

This is an exploratory study primarily intended to collect data to characterize the relationship between symptoms and voice features for participants with acute viral

respiratory illness. The data will be used to quantify changes from well to sick using voice and self-reported symptoms collected with an Electronic diary in symptomatic SARS-CoV-2/influenza virus/RSV positive participants. The hypotheses that voice and self-reported symptoms will change with acute viral respiratory illness will be tested. This data will be used as the basis to build voice and symptom algorithm(s) for detection and monitoring of these illnesses. No decision rules will be made.

5.2. General Methods

Data will be summarized using descriptive statistics (number of participants (n), mean, median, standard deviation (SD), minimum and maximum, as appropriate) for continuous (or near continuous) variables, and using frequency and percentages for discrete variables.

Participants can complete the Electronic diary multiple times per day, and each time is considered a session. The session with the most compliant voice and symptom data, and the highest quality voice data will be used for that day to compute the summary statistics. All individual sessions will be used for statistical modeling.

P-values will be generated where appropriate and any p-value < 0.10 will be considered statistically significant. Due to the exploratory nature of the study, p-values will not be adjusted for multiplicity. P-values will be rounded to 3 decimal places and therefore presented as 0.xxx; P-values smaller than 0.001 will be reported as '<0.001'.

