8.1. Efficacy Assessments

8.1.1. Electronic Diary Symptoms and Voice Assessments:

Participants will perform their voice and symptom tasks once a day. Instructions and training in the Electronic diary will guide the participants on how and when to complete these tasks. The participant will be expected to record their daily voice and symptoms until they finish the participation in the study.

The following voice and symptom assessments will be entered daily by the participant in the Electronic diary:

Daily Symptoms: Fever, cough, shortness of breath or difficulty breathing, fatigue, nasal congestion, runny nose, sore throat, loss of taste or smell, chills, muscle pain, diarrhea, vomiting, headache, nausea, rigors, wheezing. In addition, the participant will rate each of the symptoms from None, Very Mild, Mild, Moderate, Severe. The definitions of the symptoms and rating severity are provided in the Electronic diary. For fever, the definition below will be followed:

- None: less than 38.0°C or 100.4°F
- Mild (Grade 1) ≥38.0°C to 38.4°C or 100.4°F to 101.1°F
- Moderate (Grade 2) >38.4°C to 38.9°C or 101.2°F to 102.0°F
- Severe (Grade 3) >38.9°C to 40.0°C or 102.1°F to 104.0°F
- Grade 4 >40.0°C or >104.0°F
- Temperature not taken.

Daily Voice Assessments: 2 phonemes: 'eee' and 'mmm' for 4 seconds (minimum 3 seconds), 1 phoneme: "ahh" sustained (as long as possible) and a 5-sentence reading passage: "When the sunlight strikes raindrops in the air, they act as a prism and form a rainbow. The rainbow is a division of white light into many beautiful colors. These take the shape of a long round arch, with its path high above, and its two ends apparently beyond the horizon. There is, according to legend, a boiling pot of gold at one end. People look, but no one ever finds it. When a man looks for something beyond his reach, his friends say he is looking for the pot of gold at the end of the rainbow".

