5.2.2.1. Definition of Occurrence of New or Increased Symptoms

To define the first occurrence of new or increased symptoms for each participant who has no acute symptoms at enrollment, firstly the maximal total symptom score during the first 3 days with available symptom data of the participant is identified (defined as the Initial Symptom Score). The total symptom score is the sum of all the symptom responses per session converted to numeric as described in [Section 5.2.3](#). An observation is defined as the mean of the daily total symptom score across sessions for each compliant day.

Then the first occurrence of new or increased symptoms is defined as the first day after these 3 days when the observed total symptom score is greater than the Initial Symptom Score.

If no greater value in total symptom score is observed after the first 3 days with available symptom data, no occurrence of new or increased symptoms is defined, and the participant is considered as asymptomatic.

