5.2.2.3. Well to Sick Analysis

For continuous endpoints during well to sick, i.e. after first occurrence of new or increased symptoms in participants based on Electronic diary (defined in [Section 5.2.2.1](#)), the change from baseline will be summarized descriptively by day, defining the first occurrence of new or increased symptoms based on Electronic diary as day=1. For the purpose of the well to sick analysis, the baseline is defined as the average of the endpoint values during the 7-day period before the first occurrence of new or increased symptoms. If a participant has no data during these 7 days, the average of the endpoint values for the closest 3 available days prior to these 7 days will be used for the baseline.

The disease progression from well to sick will be modelled monotonically using data only up to the time before recovery, so that the potential recovery phase afterwards is excluded. The time before recovery is defined in [Section 5.2.2.2](#).

To categorize the well to sick progression during this period (from day=1 to the time before recovery), for each endpoint, the change from baseline will be summarized as follows:

- a. The number and percentage of participants who have less than two days of available data for the endpoint during this period.
- b. For each participant who has two or more days of available data for the endpoint during this period, a linear regression of the change from baseline vs. day, without intercept, will be fit. The participants without a statistically significant trend from the model will be categorized as non-responder, and number/percentage will be summarized.
- c. For each participant with a statistically significant trend from the model in b, two measures will be computed: the day at which the first maximum change from baseline value (direction determined by linear fit in b) is reached during the period (defined as Tmax), and the ratio of the maximum change to the Tmax (defined as Growth Rate). The descriptive summary of the two measures for these significantly responding participants will be presented.

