5.2.2.4. Well State Analysis

For each of the continuous endpoints during the well state, i.e. from enrollment day to the day before the first occurrence of new or increased symptoms in participants based on Electronic diary, the average of the endpoint values across all days will be summarized for the participants descriptively.

A mixed effects model will also be conducted, with participant and day as random effects, to evaluate the inter-participant variation and intra-participant day by day variation. Gender, age and race may be included as covariates to assess the effects. Estimates of the overall mean value per feature, its standard error, and 90% CI, as well as the variance components will be presented.

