5.2.2.5. Correlation Between Symptoms and Voice Features

Change from baseline in symptom, after first occurrence of new or increased symptoms and before return to well state based on Electronic diary, will be modelled using a mixed-effects model with repeated measures (MMRM) with the change from baseline in the voice feature as covariate, day (categorical factor) as fixed effect, and participant as random effect. For the purpose of this analysis, the baseline is defined as the average of the endpoint values during the period up to 7 days before the first occurrence of new or increased symptoms, and the first occurrence of new or increased symptoms at day = 1. The day of return to well state is defined as the first day after the Maximal Score Day (defined in [Section 5.2.2.2](#)) when the total symptom score is less than or equal to the Initial Symptom Score (defined in [Section 5.2.2.1](#)).

Autoregressive AR(1) variance-covariance structure will be used for the MMRM. The estimate of the coefficient for the change in voice feature, its standard error, 90% CI, and p-value will be presented.

Pearson and Spearman rank order correlations between changes in symptoms and voice features will also be computed for each participant across days. These correlations will be summarized across participants. A heatmap plot will also be presented for each of these correlations.

CCI

CCI [REDACTED]

[REDACTED]

[REDACTED]

[REDACTED]

[REDACTED]

[REDACTED]

[REDACTED]

[REDACTED]

[REDACTED]

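### Every diary session enters models built on the day, with no term for same-day repeats: the per-participant trend test becomes anti-conservative and the AR(1) covariance is ill-defined

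*SAP*

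**What the plan says.** The protocol plans one entry a day (Protocol 8.1.1: "Participants will perform their voice and symptom tasks once a day"). SAP 5.2 allows for more: "Participants can complete the Electronic diary multiple times per day, and each time is considered a session".

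The SAP then treats a multi-session day in three ways:

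- Summary statistics use the best session of the day (5.2).
- The score that defines symptom onset uses a daily average (5.2.2.1: "An observation is defined as the mean of the daily total symptom score across sessions for each compliant day").
- Models use everything (5.2: "All individual sessions will be used for statistical modeling").

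The models themselves run on days:

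- **5.2.2.3(b).** For each participant with at least two days of data, "a linear regression of the change from baseline vs. day, without intercept, will be fit". The p-value separates responders from non-responders and decides who enters the Tmax and Growth Rate summaries.
- **5.2.2.4.** The well-state mixed model is fitted "with participant and day as random effects, to evaluate the inter-participant variation and intra-participant day by day variation".
- **5.2.2.5.** Change in symptom is regressed on change in voice feature, with categorical day and random participant. "Autoregressive AR(1) variance-covariance structure will be used for the MMRM".

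The threshold in SAP 5.2 is that "any p-value < 0.10 will be considered statistically significant", without multiplicity adjustment. No model has a session term, a day-within-participant term or a rule for same-day records. The index of the AR(1) is not stated.

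**The concern.** Two sessions by one person on one day share that day's state of health and voice, so they carry less information than two sessions on different days. A model that knows only the day either treats them as independent or has no defined place for the second one.

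The responder regression and the symptom–voice MMRM both serve the primary objective. If repeats are mishandled, some participants are called responders on the strength of duplicate entries. The MMRM either stops on a singular matrix or runs with the wrong correlation pattern. In both cases the analyst has to devise a same-day rule after seeing the data.

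**Working it through.** The plan gives no error rate for these tests, so there is no figure to reproduce beyond the nominal 0.10, taken as two-sided to match the 90% intervals.

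**1. Trend test in 5.2.2.3(b).**

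Inputs from the SAP: regression of change from baseline on day through the origin, all sessions as records, threshold 0.10.

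Assumed, because the documents do not give them:

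- share of days with a second session: 10%, 30% or 100%;
- within-day correlation ρ: 0, 0.5, 0.8 or 0.95;
- period of 2, 4, 7 or 10 days;
- days independent of each other, no true trend, baseline known.

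Each session is a day effect with variance ρ plus session noise with variance 1 − ρ. Simulated rejection (40,000 participants per setting, range over the four period lengths):

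| Sessions | ρ = 0.5 | ρ = 0.8 | ρ = 0.95 |
|---|---|---|---|
| Second session on 10% of days | 0.110–0.114 | 0.118–0.125 | 0.125–0.130 |
| Second session on 30% of days | 0.127–0.135 | 0.158–0.160 | 0.170–0.189 |
| Two every day | 0.183–0.194 | 0.231–0.283 | 0.255–0.357 |
| Three every day | 0.251–0.279 | 0.325–0.405 | 0.360–0.497 |

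At ρ = 0 every setting gives about 0.10. One record per day, whether a single session or the daily mean, gives 0.096–0.104.

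Hand check: with m sessions every day the slope variance is understated by about DE = 1 + (m − 1)ρ. For m = 2 and ρ = 0.8, DE = 1.8, and 2[1 − Φ(1.645/√1.8)] = 2[1 − Φ(1.226)] = 0.22. The simulated values are higher, most of all for short periods, because repeats also add false degrees of freedom. Two days with one session each leave 2 − 1 = 1 degree of freedom (critical t 6.31). Two sessions each leave 4 − 1 = 3 (critical t 2.35).

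**2. The baseline has its own effect.** The SAP subtracts a baseline averaged over 7 days, and its error shifts every change value of a participant in the same direction. A line forced through the origin reads that shift as slope. Rejection, with two sessions every day and ρ = 0.8 where repeats apply:

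| Days | One session a day | All sessions | Daily mean |
|---|---|---|---|
| 4 | 0.14 | 0.33 | 0.15 |
| 7 | 0.19 | 0.37 | 0.20 |
| 10 | 0.23 | 0.41 | 0.25 |

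Daily averaging removes the part due to repeats and leaves the rest.

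**3. AR(1) in 5.2.2.5.**

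- *Indexed by day.* The correlation is φ^|difference in days|, so two records on one day have φ⁰ = 1 and identical rows. For records on days 1, 1, 2, 3 with φ = 0.7, the determinant is 0 and the rank is 3 of 4. The participant random effect adds the same constant to every entry, so the duplicate rows stay identical. With one record a day on days 1, 2, 3 the determinant is (1 − 0.49)² = 0.26.
- *Indexed by record order.* With two sessions a day, same-day sessions count as one step apart (φ), and the first sessions of consecutive days as two (φ²). In simulation (500 runs, 100 participants, 10 days, two sessions a day, φ of 0.3, 0.6 and 0.8), rejection at 0.10 was 0.17–0.25 with session noise at 5% of variance and 0.13–0.16 at 20%. At 50% it was 0.09–0.13, against 0.08–0.14 with one session a day, so no clear excess.

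**4. Well state in 5.2.2.4.** Take a true participant-by-day variance of 0.25, session variance of 0.10 and no shared study-day effect.

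- Day crossed with participant: day variance 0.00 and residual about 0.35, with one or with two sessions a day.
- Day nested in participant, two sessions a day: 0.25 and 0.10, both recovered.
- Day nested, one session a day: the nested term cannot be told from the residual.

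**The case against.** The study is exploratory, SAP 5.1 makes no decisions from the results, and 5.2.2.3(b) feeds only counts and descriptive summaries. The population test of well-to-sick change is the mixed model with a random participant slope, and no inflation is shown for it here. The protocol asks for one entry a day, and dropping recordings that fail quality control may remove some repeats. All of this stands. It limits the weight of the point, but the stated rule is still wrong for the two analyses named.

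Three stronger readings are tempting, and the documents do not support them:

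- *A reader might infer that the MMRM cannot be fitted.* That holds only if the AR(1) is indexed by day with no separate residual. The SAP does not state the index, and by record order the model can be fitted but is mis-specified.
- *A reader might take a false-positive rate of a quarter to a third as typical.* That needs repeats on every day and a high within-day correlation, and neither is documented. Nor is 0.10 the true comparator, given the baseline effect.
- *A reader might blame the use of all sessions for a well-state day variance that misses within-person variation.* The cause would be a crossed day term, which fails equally with one session a day. The SAP's stated purpose is compatible with nesting, and under nesting the repeats are what separate day-to-day from within-day variation.

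**Conclusion.** The point holds for 5.2.2.3(b) and 5.2.2.5. The SAP states a rule that conflicts with its own day-level models, so this is more than missing detail.

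The direction of the error in the trend test is certain whenever same-day sessions are positively correlated. Its size is not: rejection runs from about 0.11 with occasional repeats to 0.36 with two sessions every day. That range rests on assumed repeat frequency and correlation, independent days and a known baseline. The inflation from the no-intercept fit on an estimated baseline is additional and separate. For the MMRM, the covariance is singular or mis-specified according to an index the SAP leaves open.

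The well-state model needs only a clarification of nesting. With no decision rules attached, this should be corrected but does not threaten the study.

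**What to change.** - **5.2.2.3(b) and 5.2.2.5:** use one record per participant-day, the mean of the sessions that pass quality control, as 5.2.2.1 already does for the total symptom score. State that the AR(1) is indexed by day.
- **Alternative, mixed models only:** keep all sessions and add a day-within-participant random effect. The per-participant regression needs the daily record in either case.
- **5.2.2.4:** state that day is nested within participant and what the residual measures. Sessions may be kept there.
- **Reporting:** give the number of multi-session days, so that readers can see how much this matters.

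The cost is a few sentences in the SAP. The collapsed models give no estimate of within-day variance, which the nested well-state model can supply. The inflation from the origin-constrained fit on a 7-day baseline remains and has to be dealt with separately.
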